4.5.4 Vital Sign Data

For vital sign data analyses, the analysis period is active treatment (placebo-controlled and DBE) period. Vital sign parameters include body temperature, systolic blood pressure, diastolic blood pressure, heart rate, respiration rate and weight. Vital signs will be measured with the subject supine and after the subject has been resting for at least 10 minutes. The descriptive statistics for actual values will be summarized at each visit in the active treatment (placebo-controlled and DBE) period. Plot of mean vital sign values in the active treatment (placebo-controlled and DBE period) may be provided.

Summary of change from baseline including number of evaluable subjects, mean, standard deviation, median, 25% and 75% quartiles, minimum, and maximum values will be summarized at each visit in the active treatment (placebo-controlled and DBE) period. Placebo-controlled baseline will be used for early start subjects and DBE baseline will be used for delayed start analysis.

The analysis of vital signs will also focus on the incidence of clinically relevant abnormalities at any post-baseline visit in the active treatment (placebo-controlled and DBE) period. Please refer to the placebo-controlled SAP for the criteria to assess potential clinically relevant abnormalities in vital sign. The incidence and percentage of clinically relevant abnormalities

CONFIDENTIAL

The information contained herein may not be used, disclosed, or published without the written consent of Biogen MA Inc.

	Statistical Analysis Plan Dose Blinded Extension Period	V2.0
---	--	-------------

determined by each criterion will be summarized in the active treatment (placebo-controlled and DBE) period.

A listing of subjects with clinically relevant abnormalities at any post-baseline visit in the active treatment (placebo-controlled and DBE) period will also be provided. All the data in the placebo-controlled and DBE period will be listed.

Visit windows for by visit summaries

For vital sign by visit summaries, the analysis visit should be defined using windows (see Table 2 in the Appendix). For the same parameter for a subject, if there is more than 1 record in the same analysis visit window, then select the record closest to the target visit day. If there are 2 records in the same analysis visit window with the same distance from the target visit day, then select the record with the later date.

4.5.5 ECG Data

For ECG data analyses, the analysis period is active treatment (placebo-controlled and DBE) period. The descriptive statistics for actual values will be summarized at each visit in the active treatment (placebo-controlled and DBE) period. Plot of mean ECG values in the active treatment (placebo-controlled and DBE) period may be provided.

Shift from normal or unknown ECG at baseline to abnormal post-baseline ECG, will be summarized in the active treatment (placebo-controlled and DBE) group. The number of subjects with potential QTcF interval outlier post-baseline will also be summarized in the active treatment (placebo-controlled and DBE) period. The criteria of defining QTcF interval outliers is specified in the placebo-controlled SAP. For early start subjects, the placebo-controlled baseline will be used. For delayed start subjects, the DBE baseline will be used.

A listing of subjects with abnormal ECG status post-baseline in the active treatment (placebo-controlled and DBE) period will be provided. All data in the placebo-controlled and DBE period will be listed.

4.5.6 Physical and Neurological Examination

Abnormal findings during physical and neurological examinations are captured as adverse events and will be reflected in the summary of AEs.

4.5.7 C-SSRS Data

The Columbia Suicide Severity Rating Scale (C-SSRS) is an assessment that evaluates suicidal ideation and behavior. There are 5 “Yes/No” questions on suicidal ideation following the increasing severity order: (1) Wish to be dead, (2) Non-specific active suicidal thoughts, (3) Active suicidal ideation with any methods (not plan) without intent to act, (4) Active suicidal ideation with some intent to act, without specific plan, (5) Active suicidal ideation with specific plan and intent, and 6 “Yes/No” questions on suicidal behavior

CONFIDENTIAL

The information contained herein may not be used, disclosed, or published without the written consent of Biogen MA Inc.

	Statistical Analysis Plan Dose Blinded Extension Period	V2.0
---	--	-------------

following the increasing severity order: (6) Preparatory acts or behavior, (7) Aborted attempt, (8) Interrupted attempt, (9) Actual attempt, (10) Suicidal behavior, (11) Suicide (only at post-baseline visits). Another “Yes/No” question of whether the subject has engaged in non-suicidal self-injurious behavior is also collected.

The summary table for C-SSRS will be conducted for the active treatment (placebo-controlled and DBE) period. Number of subjects who answered “Yes” to each of the 11 questions post-baseline, subjects who answered “Yes” to at least one question for suicidal ideation, subjects who answered “Yes” to at least one question for suicidal behavior, and subjects who have engaged in non-suicidal self-injurious behavior will be presented.

A listing of subjects with any suicidal ideation or behavior at baseline or post-baseline will be provided for the placebo-controlled and DBE period.

4.5.8 MRI Safety Data

Brain MRI safety findings are assessed at Screening visit, Week 24, 52, 96, 148 and 4 weeks after last dose/ET visits.

The MRI safety result is classified as normal or abnormal. Shift table from normal or unknown MRI at baseline to abnormal post-baseline MRI will be summarized in the active treatment (placebo-controlled and DBE) period. The worst post-baseline record of each subject is selected. A listing of details for abnormal brain MRI findings will be presented for placebo-controlled and DBE period.

4.6 Pharmacodynamic -Imaging analysis

4.6.1 General Consideration

There are three types of imaging outcomes in the study: DaT/SPECT imaging, Neuromelanin MRI imaging and Structural MRI imaging. Please refer to the placebo-controlled SAP for details.

The analysis population for pharmacodynamic analysis is defined in Section 3.1.1. The analysis period is placebo-controlled and DBE period. That is, data from both the placebo-controlled and DBE periods will be included in the analysis. All pharmacodynamic analyses will be presented by DBE treatment group.

The following three comparisons will be evaluated for the long-term pharmacodynamic analyses of BIIB054:

- The early start 250 mg compared with the delayed start 250 mg;
- The early start 1250 mg compared with the delayed start 1250 mg.
- The early start 3500 mg compared with the delayed start 3500 mg.

The following comparisons may also be evaluated:

- The early start 250 mg compared with the pooled delayed start group;

CONFIDENTIAL

The information contained herein may not be used, disclosed, or published without the written consent of Biogen MA Inc.

	Statistical Analysis Plan Dose Blinded Extension Period	V2.0
---	--	-------------

- The early start 1250 mg compared with the pooled delayed start group;
- The early start 3500 mg compared with the pooled delayed start group

The pooled delayed start group contains all the subjects who were randomized to placebo treatment in the placebo-controlled period including those who did and who did not enter to the DBE period. There will be no multiple comparison adjustments. Data after subjects start PD symptomatic treatment will be included in the analyses.

Visit Windows for by visit analyses

For the by visit summaries and MMRM models, the analysis visit should be defined using visit windows (see Table 3 in the Appendix). If there is more than 1 value in the same analysis visit window (>1 value for the same analysis visit) for a certain parameter for a subject, then the closest record to the target visit day will be used for the by visit analysis. If they are with the same distance from the target visit day, then the record with the later time will be used for the by visit analysis.

4.6.2 By Visit Summary and MMRM Model

A prespecified set of imaging measures as well as the change from baseline will be summarized by DBE treatment groups by visit for all the visits in the placebo-controlled and DBE period.

Change or percent change from baseline in the imaging measures will be analyzed using an MMRM model for all the visits in the placebo-controlled and DBE period. For details of the model to be used please see the 1 year SAP. Adjusted means for each treatment group, pairwise adjusted differences for the comparisons, 95% confidence intervals for the differences will be presented at each visit, and p-values will be presented for the key visits of week 24, 52, 96 and 148. If the distribution of the outcome is highly skewed, p-value will be generated from the MMRM model based on the rank data. Missing data are assumed to be missing at random behind the MMRM model.

Per design, a subset of subjects will enter year 3 and 4 for a limited time. There will be some visits with too few data in year 3 and 4. If this is the case, the visits with too few data will be excluded from the MMRM analyses, Otherwise, the MMRM model will not converge. In addition, since most patients will start PD medication by year 1, most data in year 2-4 will be after PD medication. Therefore, data after subject start PD medication will be included in the MMRM analyses. Otherwise, the MMRM model will not converge.

Data at the common visits of cohort A and cohort B will be included in the by visit summary and MMRM model. Data at all visits will be listed.

4.6.3 Additional analyses of placebo-controlled period due to COVID-19

Due to COVID-19 public health emergency, considerations were made to allow week 52 assessments to be delayed up to 4 weeks. If this occurs, some of the data may not be included in the all patient week 52 analyses, as they may miss the timeline of the corresponding

CONFIDENTIAL

The information contained herein may not be used, disclosed, or published without the written consent of Biogen MA Inc.

interim database lock. However, these data are still considered in the placebo-controlled period because they are before the first dose of DBE period. Depending how much data are missing in the all patient week 52 analyses database lock, the MMRM analyses in the placebo-controlled period may be repeated by including all the available data in the placebo-controlled period.

[REDACTED]

[REDACTED]

[REDACTED]

[REDACTED]

[REDACTED]

[REDACTED]

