5.5.5 Analysis methods

The estimand of the primary analysis for imaging outcome measure is the mean difference of the change from baseline in the imaging measure at Week 52 between treatment groups in the

	Statistical Analysis Plan Placebo-Controlled Period	V1.0
---	---	-------------

pharmacodynamics population regardless of whether start of PD medication had occurred or not. Specifically, the estimand takes the following into consideration:

- A. Population: pharmacodynamics population as defined in Section 5.1.2;
- B. Variable: change from baseline to Week 52 in the imaging measure;
- C. Intercurrent events: regardless of whether start of PD medication had occurred or not;
- D. Population-level summary: difference in variable means between each active treatment and placebo group

A set of DaT/SPECT measures and [REDACTED] have been selected for the statistical analyses based on literature review and clinical inputs before the DBL. Please see Appendix VI for the listed measures.

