Data collected after subjects who have begun taking PD medication will be included in the primary analysis. Change and percent change from baseline will be summarized by visit and treatment groups using descriptive statistics. Change or percent change from baseline in the imaging measures will be analyzed using the mixed model for repeated measures (MMRM), which includes the fixed effect of the treatment group (categorical), time (categorical), interaction between treatment group and time, region (categorical), baseline imaging values (continuous), baseline imaging values by time interaction, baseline MDS-UPDRS I+II+III total score (continuous) and baseline MDS-UPDRS I+II+III total score by time interaction. An unstructured covariance matrix will be used to model the within-subject variance-covariance errors. If the unstructured covariance structure matrix results in a lack of convergence, the heterogeneous Toeplitz covariance structure followed by the heterogeneous first-order autoregressive covariance structure will be used. The Kenward-Roger approximation will be used to estimate the denominator degrees of freedom. Least square means (LSmeans) of each treatment group as well as treatment difference between each BIIB054 groups and placebo will be displayed with 95% CI and p-value at Week 52. If the distribution of the outcome is highly skewed, p-value will be generated from the MMRM model based on the rank data. In the primary analysis, missing data are assumed to be missing at random (Rubin 1976), and the PD medication is assumed to have minimal impact on the imaging measures.

The same MCP-MOD method as used in the primary analyses of MDS-UPDRS I+II+III may be used to assess and model dose-response relationship of the imaging outcomes.

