The information contained herein may not be used, disclosed, or published without the written consent of Biogen MA Inc.

	Statistical Analysis Plan Dose Blinded Extension Period	V2.0
---	--	-------------

Note: This statistical analysis plan (SAP) covers the analyses of the dose-blinded extension (i.e., long terms extension) period (Years 2-4) and the analyses across both the placebo-controlled period and the DBE period (analyses integrating the data for Years 1-4) for study 228PD201. Please refer to the separate SAP for the analyses methods and approaches for placebo-controlled Year 1 period.

1 DESCRIPTION OF OVERALL STUDY (INCLUDING DOSE-BLINDED EXTENSION (DBE)) OBJECTIVES AND ENDPOINTS

The objectives and endpoints of the study are listed below.

The secondary efficacy endpoints have been ranked based on the order of clinical importance.

Primary Objective	Primary Endpoints
To evaluate the clinical efficacy of BIIB054 via dose response using the change from baseline in Movement Disorder Society- Unified Parkinson's Disease Rating Scale (MDS-UPDRS) Total Score	Change from baseline in MDS-UPDRS Total Score (Sum of Parts I, II, and III) at the primary timepoints of Week 52 and Week 72
Secondary Objectives	Secondary Endpoints
To evaluate the clinical efficacy of BIIB054 based on MDS-UPDRS subparts	Change from baseline to Week 52 in MDS-UPDRS the subparts III, II and I (each part separately)
	Change from baseline to Week 72 and end of study in MDS-UPDRS the subparts III, II and I (each part separately)
To assess the PK profile of BIIB054	Concentration of BIIB054 in the serum
To evaluate the dose-related safety of BIIB054	Incidence of adverse events (AEs) and serious adverse events (SAEs)
To evaluate the pharmacodynamic effects of BIIB054 on the integrity of nigrostriatal dopaminergic nerve terminals	Change from baseline to Week 52 in striatal binding ratio (SBR) in the putamen, striatum, and caudate as measured by single-photon emission computed tomography (SPECT) imaging of the dopamine transporter (DaT) with ioflupane I123 (DaTscan™)
To evaluate the immunogenicity of BIIB054	Incidence and titer of anti-BIIB054 antibodies in the serum

CONFIDENTIAL

The information contained herein may not be used, disclosed, or published without the written consent of Biogen MA Inc.

	Statistical Analysis Plan Dose Blinded Extension Period	V2.0
---	---	------

Exploratory Objectives	Exploratory Endpoints

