As this study is on-going when the Covid-19 public health emergency (PHE) occurred, subject visits and data collection were impacted, including missing visits, delayed visits, missed assessments and/or some visits were performed via remote assessments, e.g. telephone/video visits. Every effort was made to document these impacted study activities systematically on the eCRF and other electronic source data.

CONFIDENTIAL

The information contained herein may not be used, disclosed, or published without the written consent of Biogen MA Inc.

	Statistical Analysis Plan Dose Blinded Extension Period	V2.0
---	--	-------------

A complete listing of all visits impacted (e.g. missed visits, delayed or assessment done via remote visits) will be listed in the clinical study report. Missing data due to Covid-19 is considered as missing at random.

Impact of COVID-19 on the clinical outcome analyses

In addition, subgroup analyses of the selected key clinical outcome MDS-UPDRS will be performed on a subset of subjects who did not have ≥ 3 consecutive missing doses throughout the study to further evaluate the impact of Covid-19 on the study. The same MMRM model for the primary analyses will be used for the subgroup analyses.

In addition, due to Covid-19, some visits were delayed. A few subjects will have their Week 52 imaging done at later visits up to Week 72 and these will still be considered as Week 52 visit data in the analyses for Week 52. These data were not included in the Week 52 database lock in time, but will be included in the Week 72 database, and the related Week 52 imaging analyses will be updated at the time of the Week 72 interim analyses.

Impact of COVID-19 on the safety analyses

During the COVID-19 pandemic period, subjects may be prone to a high risk of getting depressed or anxiety. As a result, the analyses below will be performed to evaluate the impact of the COVID-19 pandemic on the safety analyses.

1. An overall summary of AE in DBE period based on data after March 7th, 2020, the start date when subjects in SPARK get impacted by COVID-19
2. An overall summary of AE in the active treatment (placebo-controlled and DBE) period based on data after March 7th, 2020, the start date when subjects in SPARK get impacted by COVID-19
3. AEs by system organ class and preferred term sorted by decreasing frequency in DBE period based on data after March 7th, 2020, the start date when subjects in SPARK get impacted by COVID-19

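### The Week 52 DaT/SPECT secondary analysis is stated inconsistently on scale, on data cut and on which late scans count

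*SAP*

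**What the plan says.** **Scale.** The objectives tables of both SAPs give the secondary endpoint as "Change from baseline to Week 52 in striatal binding ratio (SBR) in the putamen, striatum, and caudate". The imaging estimand in Year 1 SAP 5.5.5 agrees: "Variable: change from baseline to Week 52 in the imaging measure". The model sentence in the same section reads "Change or percent change from baseline in the imaging measures will be analyzed using the mixed model for repeated measures (MMRM" and gives no rule for choosing. The dose-blinded extension (DBE) SAP repeats the wording in 4.6.2: "Change or percent change from baseline in the imaging measures will be analyzed using an MMRM model".

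**Data cut.** DBE SAP 4.6.3 opens its rule with "Depending how much data are missing in the all patient week 52 analyses database lock" and continues "the MMRM analyses in the placebo-controlled period may be repeated by including all the available data in the placebo-controlled period". It sets no threshold. Year 1 SAP 5.3.5 and DBE SAP section 5 (COVID-19 impact) both say "the related Week 52 imaging analyses will be updated at the time of the Week 72 interim analyses". Neither SAP says which run is the reported Week 52 result.

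**Late scans.** DBE SAP 4.6.3 deals with Week 52 assessments up to 4 weeks late and treats them as placebo-controlled data because they precede the first DBE dose. Year 1 SAP 5.3.5 and DBE SAP section 5 count imaging at later visits, as late as Week 72, as Week 52 data and do not require that it precede DBE dosing.

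**Timing and error control.** Year 1 SAP section 6 gives a small sponsor team, separate from study management, the unblinded 1-year results; the Week 72 analysis comes later. No multiplicity adjustment applies to secondary endpoints.

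**The concern.** With no alpha protection, pre-specification is the only safeguard this endpoint has, and it is incomplete in three places. The tested scale can depart from the estimand. The repeat on fuller data is optional in one section and mandatory in two others, and falls after the 1-year unblinding. The late-scan rules disagree on more than a date. Week 52 is the first DBE dosing visit (Year 1 SAP 3.1.1), and placebo subjects are re-randomised to BIIB054 before that infusion (3.1.2). Under the wider rule, a former placebo subject's Week 52 scan could follow active drug, so the two data cuts may differ in meaning as well as in size.

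**Working it through.** Neither SAP states a power or error rate for the SBR comparison, so there is no planned figure to reproduce. The check has two parts.

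**1. The passages side by side**

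- *Scale.* Endpoint and estimand: change. Model sentence: change or percent change. The sentence before it in Year 1 SAP 5.5.5 summarises both scales descriptively and joins them with *and*; the model sentence uses *or*. It therefore reads as an alternative, and it conflicts with the estimand.
- *Data cut.* A scan 3 weeks late that missed the first lock falls under both rules. DBE SAP 4.6.3 says the analysis *may* be repeated to include it; section 5 of the same document says the analysis *will* be updated.
- *Late scans.* The allowed delay is 4 weeks in one rule and 72 − 52 = 20 weeks in the other. At one infusion every 4 weeks, a subject dosed on schedule receives BIIB054 at Weeks 52, 56, 60, 64 and 68, which is five infusions before a Week 72 scan.

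**2. Size of the error-rate effect if the better result were always reported**

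Inputs from the SAP: 91 placebo and 90 subjects in the 3500 mg arm (Year 1 SAP Table 4.3); two-sided 0.05; SD of change 0.156 (Year 1 SAP section 6, for ipsilateral putamen; that section sets it against a variance symbol but calls it an SD, and it is taken as an SD here).

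Assumptions not in the SAP: baseline SBR mean (SD) 1.2 (0.30) or 0.8 (0.25); mean decline 8% of baseline; noise constant or proportional to baseline; 3%, 10% or 20% of scans missing at random from the first lock. Of 181 subjects these shares are about 5, 18 and 36. The SAP says only that a few subjects are late.

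Model: ANCOVA on baseline b, one dose against placebo, 8,000 null runs per setting. Monte Carlo standard error: √(0.05 × 0.95 / 8000) = 0.0024. With constant noise,

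- change = −0.08b + σz
- percent change = 100(−0.08 + σz/b)

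The intercept and the baseline term absorb the decline, and σ cancels from each t statistic. The same holds for proportional noise. The results therefore do not depend on 0.156 or on the 8%, only on the baseline spread, the noise form and the late share.

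Chance of at least one p < 0.05, range over the four baseline and noise settings:

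| Late scans | Choice of scale | Choice of data cut | Both |
|---|---|---|---|
| 3% | 0.058–0.067 | 0.051–0.058 | 0.066–0.076 |
| 10% | 0.059–0.067 | 0.062–0.067 | 0.075–0.087 |
| 20% | 0.061–0.065 | 0.068–0.075 | 0.089–0.092 |

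Each single test, with scale and cut fixed in advance, had size 0.044–0.055, consistent with 0.05. Four independent tests would give 1 − 0.95⁴ = 0.185; the four here are highly correlated, so the inflation is far smaller. A second simulation (90 per arm, baseline mean 0.8, CV 0.3–0.4, 2–10% late) gave 0.056–0.071 for scale, 0.055–0.065 for data cut and 0.071–0.084 for both.

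**The case against.** The strongest reply is that the plan is tighter than it looks. The estimand fixes change from baseline, so the model sentence is loose drafting that covers all imaging measures. That stands: the scale is not wholly open. The loose sentence still governs the test and contradicts the estimand. Appendix VI is blacked out and might say more, but 5.5.5 cites it only for the list of measures.

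On the data cut, the governing Year 1 SAP says the update will happen, and an update would ordinarily replace the earlier result. DBE SAP 4.6.3 could be read as an extra analysis of a narrower set of scans. That is a fair reading, but the sets overlap, no text says that the later result supersedes, and the narrower rule is the one that protects the placebo comparison.

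DBE SAP 4.6.2 is the long-term early-start versus delayed-start model, so it is a secondary location; Year 1 SAP 5.5.5 is the sentence that matters.

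A reader might infer that the sponsor plans to pick the better p-value after unblinding. The documents do not support that: the stated trigger is the amount of missing data, not the result, and the unblinded team is separate from study management. Nor do they support a threat to the trial's overall type I error, because SBR lies outside the 0.04/0.01 scheme for the primary endpoint.

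The simulated figures are also a worst case. They assume the better result is always reported, use ANCOVA in place of the planned MMRM, and rest on assumed baseline values and late shares.

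**Conclusion.** The point holds as an inconsistency in a named secondary endpoint. The tested scale conflicts with the estimand, optional and mandatory repeats conflict, no reported data cut is named, and the two late-scan rules are incompatible. The late-scan conflict matters most for interpretation, because the wider rule can bring scans taken on BIIB054 into the placebo arm.

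The error-rate consequence is modest: from a nominal 5% to roughly 6–7% for scale, about 5–6.7% for data cut with 3–10% late scans, and about 7–9% for both, the top of that range needing 20% late. If only a few scans are late, the data-cut part stays close to nominal (5.1–5.8% at 3%). These figures assume selection of the better result, which the text permits but does not plan. No confirmatory claim is affected. The passages should be corrected because the inconsistencies are real and cheap to remove.

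**What to change.** - **Scale.** In Year 1 SAP 5.5.5, and in DBE SAP 4.6.2 to match, run the MMRM test on change from baseline, as the estimand states. Keep percent change as descriptive or supportive.
- **Data cut.** Reconcile DBE SAP 4.6.3 with Year 1 SAP 5.3.5 and DBE SAP section 5. Name one cut as the reported Week 52 SBR result and show the other as a sensitivity analysis. The Week 72-lock update is the natural choice, since two sections already commit to it. Remove the unquantified missing-data condition.
- **Late scans.** State one rule in all three places: scans taken after the first DBE dose do not enter the reported placebo-controlled comparison. They can be shown in a sensitivity analysis. Asking for all eligible data would not be enough, because eligibility is what the passages disagree on.

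The cost is wording only: the update is already planned and percent change is still shown. If the 1-year results have already been seen when the text is changed, the amendment should say so and both cuts should be reported.
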